We will identify UC and CD using algorithms validated for accurately identifying these conditions from primary care records in the UK. We will identify a prevalent cohort of adults with IBD with the RCGP RSC network over the last decade. We will identify a matched cohort of people without IBD; matched on age, gender and primary care practice. Across these cohorts we will compare healthcare resource utilisation (primary care attendances, number of primary care prescriptions for antidepressant and anxiolytic medications, number of primary care prescriptions for medications used in IBD, recorded secondary care attendances, and issue of statements of fitness for work), incident infections (any common infection, any viral infection, or any gastrointestinal infection), and common mental health conditions (depression, anxiety, and attention deficit hyperactivity disorder).

Lay Summary

Ulcerative colitis and Crohn's disease are the commonest types of inflammatory bowel disease (IBD). Both conditions range in severity from no symptoms to being potentially fatal. Both conditions are treated with medications which suppress the immune system. It is not known whether this increases the risk for infections in these conditions. It is also recognised by healthcare professionals that these conditions cause a considerable amount of psychological distress. However, this has never been measured in a large population sample.

These studies will investigate any associations with treatment and new onset infections. They will also examine the relationship between IBD and common mental health problems (specifically, depression and anxiety) and the impact that these have on the healthcare use (including number of GP appointments, hospital attendances, and medication prescriptions). Combined, these studies should provide a better understanding of the impact of IBD on affected people and provide evidence to support the correct allocation of healthcare resources.

Introduction

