3. We aim to describe the prevalence of common mental health conditions (anxiety, depressive episodes, and recurrent depressive disorder) in people with IBD when compared to an age and gender matched cohort.
4. We aim to explore healthcare utilisation in individuals with IBD with and without common mental health problems.

Methods

Study design

We aim to perform a retrospective matched cohort study. We will match people with UC and CD, to people without IBD. A history of common mental health conditions was assessed at baseline (matching date) in both cohorts, and compared. Both cohorts will be followed-up (retrospectively) from the matching date for incident infections, and healthcare resource utilisation.

Data source

We aim to use the Royal College of General Practitioners (RCGP) Research and Surveillance Centre (RSC) database. This database contains the pseudonymised primary care records of the registered population all from a network of GP practices which provide a representative sample of the UK population.⁹ The RCGP RSC database contains complete data on all events and clinical entities coded in UK primary care. These include demographic information, clinical diagnoses, laboratory test results, primary care issued prescriptions, process of care codes (e.g. specialist referrals), and anthropometric measurements (e.g., body mass index; BMI), and are coded using the Read coding system.¹⁰

UK general practice records provide several advantages for this study type;^{11, 12} UK primary care is a registration-based system (a patient can only register with a single GP), records have been computerised since the 1990s, and pay-for-performance targets (introduced in 2004 through The Quality and Outcomes Framework; QOF) have resulted in consistent high-quality clinical data entry about chronic disease. Studies using the RCGP RSC data have been published across a range of chronic diseases.¹³⁻¹⁵ RCGP RSC practices get feedback on their data quality, including using a dashboard. A particular emphasis of this feedback is “episode typing” – designating cases first, new, or ongoing – which helps differentiate incidence from prevalence.¹⁶

Study population and outcome measures

All adults (aged ≥ 18) registered with a GP practice contributing to the RCGP RCS at the time of data extraction will be eligible for inclusion.

Definition of the IBD cohort

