All individuals with one or more diagnostic codes for UC or CD prior to the study start date were eligible for inclusion in the IBD cohort. The use of diagnostic codes to identify IBD from UK primary care records has been validated and shown to be accurate and to correctly differentiate between UC and CD.^{17, 18} The Read codes used to identify UC and CD were based on the codes list used by Abrahami et al.,¹⁸ and mapped to both Read code versions used within the RCGP RSC network (Appendix 1). The use of diagnostic codes to identify IBD has also been shown to have good validity in US claims databases.¹⁹

Definition of the matched cohort

The matched unexposed cohort will be identified by matching individuals with IBD to people without IBD. Matching will be performed on age and gender as a minimum. Follow-up for each matched individual will begin at the same baseline date as those with IBD.

Infections outcomes

Infections outcomes will comprise:

1. The time to first recorded presentation with a new episode of any common infection during the study period; a composite of upper respiratory tract infections, pneumonia, bronchitis, influenza-like illness, skin infections, genital infections, urinary tract infections and gastrointestinal infections.
2. The time to first recorded presentation with a new episode of any viral infection.
3. The time to first recorded presentation with a new episode of any episode of gastrointestinal infection.

The Read codes used to identify infections will be adapted from the validated indicators used in routine surveillance by the RCGP RSC. The chosen infections in the composite infections outcomes were selected principally as they represent the majority of the primary care adult infectious disease burden, and include a mixture of viral, bacterial and fungal infections. First or new episodes of an infection are coded accordingly in the database, enabling differentiation from chronic infections or follow-up visits for the same episode. If available, we will also explore type and pathogens contributing to the incident infections.

Mental health outcomes

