The presence of common mental health conditions at baseline will be determined for the case and control cohorts. We will examine three groups of common mental illness as defined by the International Statistical Classification of Diseases and Related Health Problems 10th Revision (ICD10) classification;²⁰ depressive episodes (F32), recurrent depressive disorder (F33), and non-phobia related anxiety disorders (F41). These conditions are chosen as they represent the most common mental health conditions presenting to primary care.²¹ These conditions will be identified using algorithms validated in UK primary care.²² We selected the algorithms used here (Appendix 2) to optimise the positive predictive value. In brief, we will use a concurrent diagnosis and treatment code to identify acute episodes (depressive episodes and anxiety episodes) and for recurrent depression either a historical code for any depression and current treatment or a recurrent

depression specific diagnosis code (Appendix 2). As a secondary analysis we will also explore the prevalence of attention deficit hyperactivity disorder (ADHD) in the case and control cohorts.

Healthcare utilisation outcomes

The components of healthcare utilisation to be examined comprise; number and duration of primary care attendances, number of primary care prescriptions for antidepressant and anxiolytic medications, number of primary care prescriptions for medications used in IBD, recorded secondary care attendances, and issue of statements of fitness for work (also termed fit notes or sick notes).

Antidepressant medication classes to be examined comprise, selective serotonin reuptake inhibitors (SSRIs) and related medications (serotonin and norepinephrine reuptake inhibitors; SNRIs), tricyclic antidepressants (TCAs) and related medications (tetracyclic antidepressant TeCAs), and monoamine oxidase inhibitors (MOAIs). Anxiolytic medications to be examined comprise all benzodiazepines and other related medications indicated for use in anxiety states (Appendix 3). Medications used for the treatment of IBD to be examined will comprise; topical 5-aminosalicylic acid (5-ASA) medications, topical glucocorticoids, oral 5-ASA medications, oral glucocorticoids, non-biologic immunosuppressant medications (cyclosporine, azathioprine, mercaptopurine, methotrexate), and biologic therapies (Appendix 3).

Other baseline measures

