Socioeconomic status will be defined using the official national measure; the index of multiple deprivation (IMD).²³ This is calculated at the point of data extraction, using patient postcode, with the resultant scores stratified by deprivation quintile. Ethnicity will be extracted from the primary care record and grouped into major ethnic groups; white, black, Asian, mixed, and others.²⁴ BMI will be defined as the most recently recorded measurement prior to the study start date. Smoking status will be defined using the most recently recorded data prior to the study start date. Diagnosis codes will be used to define the presence of comorbidities at baseline; diabetes, hypertension, atrial fibrillation, angina, myocardial infarction, congestive heart failure, stroke, transient ischaemic attack, chronic kidney disease (stages 3–5), dementia, rheumatoid arthritis, chronic liver disease, asthma and chronic obstructive pulmonary disease (COPD).

Statistical Analyses

Comparison of the prevalence of mental health conditions

We will compare the prevalence of the three common mental health conditions in people with IBD and matched controls prior to the baseline date (January 1, 2015). We will stratify groups by age, and gender, and for those with IBD by condition (UC or CD) and duration of disease, and other important baseline factors. We will evaluate differences in baseline characteristics between the cohorts using the χ^2 test for categorical variables and the unpaired t-test for continuous data. Other statistical tests may be used if appropriate, depending on the data type and distribution.

Comparison of healthcare utilisation

We will compare the measures of healthcare utilisation between people with IBD and matched cohorts over a follow-up period. Follow-up will end at the earliest of; the study end-date (data extraction date), the date of patient transfer from an included practice, or date of death. All individuals contributing at least 1 day of follow-up will be included for analysis. We will stratify and compare healthcare utilisation in people with IBD by age and gender, condition (UC or CD), duration of disease, the presence of mental health conditions, and other important

confounders. All utilisation outcomes will be adjusted for the duration of follow-up and reported as event rates.

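### Registration is not tied to the 2015 baseline and no look-back is set, so pre-baseline records may be shorter in comparators and could inflate the Aim 3 mental-health contrast

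*Combined protocol and SAP*

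**What the plan says.** - **Eligibility, both cohorts** (Methods, Study population and outcome measures): adults "registered with a GP practice contributing to the RCGP RCS at the time of data extraction". Nothing is asked about registration at or before baseline.
- **IBD cohort** (Definition of the IBD cohort): "All individuals with one or more diagnostic codes for UC or CD prior to the study start date".
- **Matched cohort** (Definition of the matched cohort): "Matching will be performed on age and gender as a minimum", with the same baseline date as the IBD members. The Abstract says "matched on age, gender and primary care practice". Neither names registration date or record length.
- **Mental-health outcome**, worded three ways:
  - Study design: "A history of common mental health conditions was assessed at baseline (matching date) in both cohorts".
  - Mental health outcomes: "The presence of common mental health conditions at baseline will be determined for the case and control cohorts".
  - Statistical Analyses: prevalence in people with IBD and "matched controls prior to the baseline date (January 1, 2015").
- **Case definitions** (Appendix 2, table S2): depressive episodes and anxiety each need a code together with concurrent treatment. Recurrent depression needs either a specific code, or a depression code more than 1 year old plus current treatment. That 1-year split is the only time boundary given.

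**The concern.** A dated IBD code shows that some record exists from before the study start. A comparator needs no such evidence. Read literally, someone who joined a practice after 1 January 2015 could serve as a comparator, and with no earlier history on file would count as free of mental illness. If this is more common among comparators than among IBD members, the Aim 3 prevalence ratio rises with no true difference behind it.

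The outcome is also not pinned down. From the same text, two analysts could produce lifetime recorded prevalence, period prevalence or point prevalence. That gap remains even if the bias is nil. It carries into Aim 4, which splits people with IBD by mental-health status. Baseline comorbidities likewise have no stated window.

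**Working it through.** The documents give no prevalence, record length, matching ratio or sample size, so there is no figure of the plan's to reproduce. The check sets the rules side by side and then runs sensitivity calculations on assumed inputs.

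**Step 1. Rules by cohort** (study start, matching date and baseline are taken as the same date, which the plan implies but does not state)

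| Rule | IBD | Matched |
|---|---|---|
| Registered at or before baseline | not required | not required |
| Coded event before study start | required | not required |
| Minimum prior registration | none | none |
| Look-back window for mental health | none | none |
| Matching on or adjustment for record length | none | none |

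The only asymmetry is the second row, and it is indirect.

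**Step 2. Short records in comparators.** Let p be the share of comparators with a short record and c the share of their true history that is captured. Assume complete IBD records and a true ratio of 1. The false prevalence ratio is 1/[1 − p(1 − c)].

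- p = 0.03, c = 0.5: 1/0.985 = 1.015
- p = 0.08, c = 0: 1/0.92 = 1.087
- p = 0.12, c = 0: 1/0.88 = 1.136
- any p, c = 1 (history complete whatever the registration date): 1.000

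If a share p1 of IBD members also have short records, the ratio is [1 − p1(1 − c)]/[1 − p(1 − c)]. With p = 0.08, p1 = 0.04 and c = 0 it is 0.96/0.92 = 1.043. With p1 = p it is 1.000.

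**Step 3. Imbalance from the IBD-code rule alone.** Assume that record length is exponential with mean m years and that mental-health codes arise at rate λ per year. A share q of IBD codes is on file from registration, and the rest appear at rate g per year. Write E(a) = 1/(1 + a·m). Take m = 10, λ = 0.02, g = 0.1.

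- Comparators: 1 − E(λ) = 1 − 1/1.2 = 0.1667.
- IBD, q = 0: [1 − E(g) − E(λ) + E(g+λ)]/[1 − E(g)] = (1 − 0.5 − 0.8333 + 0.4545)/0.5 = 0.1212/0.5 = 0.2424. Ratio 1.455.
- IBD, q = 0.5: (0.5 × 0.1667 + 0.5 × 0.1212)/(0.5 + 0.5 × 0.5) = 0.1439/0.75 = 0.1919. Ratio 1.152.
- IBD, q = 0.9: (0.9 × 0.1667 + 0.1 × 0.1212)/(0.9 + 0.1 × 0.5) = 0.1621/0.95 = 0.1706. Ratio 1.024.
- q = 1: ratio 1.000.

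Over m = 5 or 10, g = 0.1 or 0.5 and λ = 0.01 to 0.04, the false ratio is 1.16–1.65 at q = 0, 1.07–1.16 at q = 0.5, 1.01–1.03 at q = 0.9, and 1.00 at q = 1. It is never below 1, but the model only lets the code rule lengthen IBD records.

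**Step 4. With equal windows.** If both cohorts are limited to people registered for the whole of one fixed window of L years, both have coded prevalence 1 − exp(−λL), and the false ratio is 1.00 by construction. At λ = 0.02 the prevalence is 2.0%, 5.8% and 9.5% for L = 1, 3 and 5.

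**Step 5. Window against table S2.** Someone with no more than 12 months of coded history cannot hold a depression code more than 1 year old, so a 12-month minimum cannot support that recurrent-depression route.

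**The case against.** The strongest reply is that neither cohort has a prior-registration rule, so the plan treats them alike. A recent registrant whose IBD code arrived with a transferred history qualifies as readily as a recent registrant without IBD. The Data source section describes the database as complete for coded events and UK records as computerised since the 1990s. If history travels with the patient, the artefact vanishes. This stands as a limit on what can be claimed. It does not close the gap, because a description of database content and a computerisation date do not say that each person's history before the current registration is on file.

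Follow-up from a shared baseline, with censoring at transfer out, presupposes that comparators are under observation at baseline. That may well be the intent, but no eligibility line says so. The phrase about data extraction could also attach to the practice's contribution rather than the person's registration. In that case registration has no date at all, and the gap remains. Matching on practice, if the Abstract governs, would align practice-level record start but not individual record length.

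A reader might infer four stronger things that the documents do not support:

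- That IBD members must have prior registration and comparators need none. IBD members need only a dated code.
- That upward bias is established. It is an inference about data the plan does not describe.
- That table S2 counts any coded episode of depression or anxiety. It also requires concurrent treatment, and if presence at baseline means current status, look-back length matters less. A different time basis for recurrent depression is not in itself an error.
- That Aim 3 is distorted through comorbidity adjustment. Comorbidities are named as factors only in the infection analysis.

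**Conclusion.** The concern holds as a design gap with a possible, not demonstrated, bias. Eligibility is not anchored at baseline, only IBD members must have an earlier coded event, and nothing equalises or describes record length. If there is a bias from this source, the likely direction is towards higher apparent mental-health prevalence in IBD.

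Its size is unknown. Under the short-record assumptions it runs from none to about 14%, and the upper end needs 12% of comparators with no captured history and complete records in every IBD member. The second model runs from none to 65%, the latter only if no IBD code is on file at registration. These are illustrations, not estimates; the spread shows that the documents do not bound the effect. The unsettled outcome wording is a defect whatever the size.

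**What to change.** 1. Require registration at the baseline date, and the same minimum continuous prior registration, in both cohorts: at least 12 months, and longer than 12 months for the recurrent-depression route that needs a code more than 1 year old.
2. State one look-back window for mental-health status, applied identically to both cohorts, and use one wording throughout. Whether the main measure is 12-month period prevalence or recorded history is the sponsor's choice, provided it is stated.
3. Report the distribution of pre-baseline record length by cohort, and say whether history from before the current registration is in the extract.
4. Give ever-recorded prevalence matched on or adjusted for record length, since a minimum registration rule alone does not equalise an open-ended look-back.
5. State the look-back for baseline comorbidities too.

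The cost is a few lines of eligibility and definition text and one descriptive table. The downside is that some recently registered people are lost. A fixed window would also give lower absolute prevalence than ever-recorded history.

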Ulcerative colitis (UC) and Crohn's disease (CD) are chronic inflammatory conditions collectively termed inflammatory bowel disease (IBD).¹ In both conditions there is a spectrum of disease ranging from a quiescent state with few or no symptoms to potentially fatal disease. Both conditions commonly require extensive medical intervention over many decades of disease and may also require substantial surgical treatment.^{2, 3} With the global burden of IBD rising, calls have been made for improved treatment options,⁴ and these been met with the development of a range of biologic therapies.¹

Current treatment strategies for UC focus on the use of immune modulating medications. Whilst frequently effective for disease control, these treatments have the potential to increase the risk of common infections,^{5, 6} which includes both common and atypical pathogens.⁶ An understanding of the infection risk in a community-based population with UC is therefore important. However, the existing literature on infection rates in people with UC has focused almost exclusively on secondary care populations. It therefore remains unclear what the total burden of infectious disease is in a population-based cohort with UC and how this compares to those without UC.

Despite increasing treatment options, quality of life is significantly reduced in people with IBD⁷ and the prevalence of mental health disorders has been reported to be higher in children with IBD.⁸ However the magnitude of any potential association between IBD and mental illness in adults has not yet been fully explored.

Given the prolonged course of medical treatment in IBD, it is important for payers to have a good understanding of the total healthcare utilisation of people with IBD. Again, in this area, existing studies have focussed on secondary care based cohorts. Little is known about healthcare resource utilisation in primary care, in people with IBD, in the UK.

Aims

1. We aim to describe the incidence of common infections in a population of individuals with IBD, compared to a matched control population without IBD. We will explore all common infections and also focus on viral and gastrointestinal infections.
2. We will explore how incidence of infection varies by age, and other factors associated with risk of infection in IBD including medication use.

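### Infections count only when presented to and coded by the GP, contact with the practice may differ between the groups compared, and no infection analysis addresses unequal detection

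*Combined protocol and SAP*

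**What the plan says.** Infections outcomes defines the composite as "The time to first recorded presentation with a new episode of any common infection during the study period" and the second outcome as "The time to first recorded presentation with a new episode of any viral infection"; the gastrointestinal outcome follows the same pattern. Under Data source, the database "contains complete data on all events and clinical entities coded in UK primary care", so an infection enters the study only if it reaches the practice and is coded there. The composite puts upper respiratory infection, influenza-like illness and skin infection together with pneumonia, and the choice is justified by primary care load: "The chosen infections in the composite infections outcomes were selected principally as they represent the majority of the primary care adult infectious disease burden".

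Comparison of infections plans incidence per 1000 person-years and Cox models, and describes the result as risk of infection. The factors named are age, gender, deprivation, size of household where available, comorbidity and UC drugs.

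Separately, Healthcare utilisation outcomes states: "The components of healthcare utilisation to be examined comprise; number and duration of primary care attendances". Comparison of healthcare utilisation compares these measures between the cohorts, and within the IBD cohort by several characteristics. Neither section connects attendance to the infection analysis.

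**The concern.** Mild infections are often managed at home. Whether one is recorded depends on whether the person consults, and partly on whether the person is at the practice for another reason while it lasts. If one group has more contact, more of its minor infections are recorded even when the true rates are equal. In a time-to-first-event composite, common minor illness will tend to supply most of the events, which is where recording depends most on contact.

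Aim 2 faces the same problem. Medication use is taken from primary care prescriptions, so exposure and outcome come from the same contact-generated record. If treated IBD patients are seen more often than untreated ones, a medication signal could arise from recording alone. At stake is whether a modest hazard ratio can be read as infection risk, which is how the analysis section phrases it, or only as a difference in recorded presentations.

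**Working it through.** The documents give no sample size, infection rate, attendance rate, matching ratio or expected effect, so there is no figure of the plan's own to reproduce. The inputs in steps 1 to 3 are assumptions, used to show a range.

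1. **Basic relation.** Let the true hazard be λ in both cohorts, and let d1 (IBD) and d0 (matched) be the probabilities that an infection is presented and coded, independent of its timing. The recorded hazard is λ × d, so the recorded HR is d1/d0.
   - 0.33/0.30 = 1.10; 0.375/0.30 = 1.25; 0.45/0.30 = 1.50.
   - With the roles reversed, 0.30/0.33 = 0.91.
   - This applies to the contact-dependent part of the composite. If a share f of the matched cohort's recorded hazard is contact-dependent with ratio r, and the rest has ratio 1, the composite HR is f × r + (1 − f), which lies closer to 1.

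2. **Linking recording to visits.** Take d = s + (1 − s)(1 − exp(−v × w/365)), where s is the chance of consulting because of the infection, v is other GP visits per year, and w is the number of days in which such a visit would pick it up. For s = 0.2 and w = 14:
   - v = 5: d0 = 0.2 + 0.8 × (1 − exp(−5 × 14/365)) = 0.340.
   - v = 7.5: d1 = 0.2 + 0.8 × (1 − exp(−7.5 × 14/365)) = 0.400.
   - Recorded HR = d1/d0 = 1.178 (unrounded inputs).

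   Over s = 0.1 to 0.3 and w = 7 to 14 days, with 5 visits a year in the matched cohort, the recorded HR with no true difference is:
   - 1.03 to 1.11 for 6 visits a year in IBD;
   - 1.08 to 1.26 for 7.5 visits;
   - 1.16 to 1.50 for 10 visits.

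3. **When such an HR would look significant.** Schoenfeld's formula is events = (1.960 + 1.282)² / [p(1 − p)(ln HR)²], with two-sided 5%, 90% power and p the IBD share.
   - HR 1.10: 10.507/(0.25 × 0.009084) = 4,627 events at 1:1; 10.507/(0.16 × 0.009084) gives 7,230 at 1:4 (rounded up).
   - HR 1.20: 1,265 events at 1:1; 1,976 at 1:4.

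   With no cohort size in the documents, significance of a detection-only HR is possible but not established.

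4. **Safeguards already in the plan.**
   - Episode typing ("First or new episodes of an infection are coded accordingly in the database") separates new episodes from follow-up visits. It does not recover infections that were never presented.
   - Matching on practice appears in the Abstract; the Methods commit only to age and gender as a minimum. If done, it deals with coding differences between practices, not between people who attend more or less often.
   - The factor list is worded as open, but nothing in it concerns contact.

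**The case against.** A reader might infer that the study itself expects people with IBD to attend the GP more. The documents do not support that. The Introduction says "Both conditions commonly require extensive medical intervention over many decades of disease", which concerns medical intervention in general and stands beside surgery, and the same section says "Little is known about healthcare resource utilisation in primary care, in people with IBD, in the UK". Nor do the documents say that patients on immunosuppressants are seen more often. The direction is therefore unknown: the bias is nil if attendance is similar, and reversed if IBD infections are handled in hospital and not coded by the practice. This part of the objection stands.

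Three further points have force. For describing primary care load, recorded presentation is the quantity of interest, so the problem bites only where the plan speaks of infection risk. The figures above rest on assumed recording probabilities and visit rates, and a large hazard ratio would be hard to explain by detection alone. The viral outcome is not itemised, so how much of it is contact-dependent cannot be judged.

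The plan also offers partial help. Gastrointestinal infection is analysed separately, infection type will be explored if available, and the attendance comparison would show any imbalance. None of this tells a reader how far an infection hazard ratio depends on that imbalance.

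**Conclusion.** The point holds as a gap in the analysis plan. Every infection outcome requires presentation and coding, contact with the practice may differ between the groups compared, and no planned infection analysis addresses it. On the assumptions shown, detection alone could give a hazard ratio of about 1.03 to 1.50 if IBD attendance were 1.2 to 2 times that of the matched cohort (6/5 to 10/5 visits), or a ratio below 1 if recording were lower in IBD. These are illustrations and not estimates for this study.

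It does not follow that a raised hazard ratio would be an artefact, or that upward bias should be presumed; the documents supply neither size nor direction. This is an inexpensive improvement worth making before analysis. It is not a flaw that invalidates the main comparison.

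**What to change.** In Comparison of infections, keep the main hazard ratio as it is and pre-specify beside it:

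- **(a)** A sensitivity hazard ratio adjusted for the primary care attendance rate in the 12 months before the baseline date. No minimum prior registration is required, so either express attendance per registered time or restrict to people with 12 months' prior registration. Do not use visits during follow-up, because infections themselves cause visits. Apply the same adjustment to the medication comparison in Aim 2.
- **(b)** Separate hazard ratios for contact-dependent minor infections (upper respiratory, influenza-like illness, skin) and for pneumonia, with the precision of the pneumonia estimate reported.

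Use no pass/fail rule. If the hazard ratio attenuates materially in (a), or the excess is confined to minor infections in (b), word the conclusion as a difference in recorded presentations and not in infection risk.

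The cost is one pre-baseline count from a source already in use and a few extra models. There are two drawbacks. Prior attendance partly reflects disease severity, so (a) may over-adjust and should stay a sensitivity analysis. Pneumonia events may be sparse, so a wide interval there should not be read as absence of an excess. The plan promises public registration before analysis begins, so both additions should be written in before then.
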